9.2 SAMPLE SIZE CALCULATION

No clinical trials have been published comparing duration of therapy for unselected patients with type 1 myocardial infarction. However, most patients with type 1 myocardial infarction now undergo early percutaneous coronary intervention. From meta-analysis of stent trials comparing ≤ 6 months with 12 months of dual antiplatelet therapy [Palmerini et al, 2015] (among whom a large proportion of patients had acute coronary syndrome), the point estimates of the hazard ratios for all-cause mortality, non-cardiac mortality and bleeding were 0.87, 0.83 and 0.58 respectively. Over a 5-year period (2006-2010) in Scotland 25.4% of patients died within one year of acute coronary syndrome of whom 7.6% died from a non-cardiovascular cause, and 0.92% had a fatal bleed.

The study has been powered to assess the primary endpoint of all-cause mortality across the combined medical therapy and percutaneous coronary intervention with drug-eluting stent arms (92.5% of the study population). Assuming a more conservative relative risk reduction of 10% (risk ratio 0.9), and that patients who consent to participate in the study have a one-third lower overall risk of mortality than unselected patients, shorter durations of therapy would lead to an absolute difference of 1.69% ($0.1 \times 0.254 \times 0.667$) from the 12-month duration of treatment rate of 16.9%. A sample size of 8,472 patients per group (16,944 overall) would provide 85% power to detect this difference at two-sided $P<0.05$ (Stata 15.1 procedure 'power two-prop' without continuity correction). Given that this is an outcome ascertained by record linkage for geographically highly stable populations, we anticipate close to zero loss to follow up. To achieve the 16,944 across combined medical therapy and percutaneous coronary intervention with drug-eluting stent arms (92.5% of the study population) we need to randomise $16,944/0.925 = 18,318$ participants. In addition, the study will have slightly increased power by using not just the occurrence of the event but also incorporating the time-to-event using log-rank statistics (and Cox proportional hazards models to adjust for baseline covariates).

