4.6 Secondary outcomes

The interpretation of trial findings for secondary outcomes will focus on the effect size and 95% CI. No formal adjustment will be made to significance levels to allow for multiplicity.

For each of the following secondary outcomes (appendix C), events are defined as the time to first outcome event during follow-up from date of the index myocardial infarction. Follow-up will be censored at competing causes of death or 15 months from date of MI, whichever occurs first.

Efficacy

- Cardiovascular death and non-fatal myocardial infarction
- Cardiovascular mortality (cardiac and non-cardiac)
- Myocardial infarction (fatal and non-fatal)
- Stent thrombosis
- Coronary revascularisation
- Thrombotic stroke

Safety

- Non-cardiovascular death (including fatal bleeding) and major non-fatal bleeding
- Non-cardiovascular death (including fatal bleeding)
- Major fatal and non-fatal bleeding
- Hospitalisation for bleeding
- Intracranial haemorrhage
- Gastrointestinal bleeding

The analysis will follow that specified for the primary outcome in section 4.5. The number and proportions of participants with an event for individual components of the secondary outcomes will also be reported alongside the composite.

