4.6.1 Sensitivity analyses

Competing risk of death

To take into account the possibility of a competing risk of death, a Fine and Gray[3] proportional sub-distribution hazards regression model will be used to take into account the competing risk of death to provide reassurance about the robustness of the analysis. The effect of the randomised intervention will be presented by the sub-distribution hazard ratio and 95% confidence interval. The cumulative incidence function (CIF) obtained from the Fine-Gray model will be plotted separately for each intervention; the median time to event and its 95% CI will be reported by intervention group. The absolute risk difference (and its 95% CI) will also be reported at the median time to event.

Diagnostic position

The analysis of secondary safety outcomes, will consider the occurrence of an event if the diagnostic codes, as defined in Appendix C, occur in any diagnostic position.

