Appendix C

Outcomes defined used the following codes and positions specified below following the date of index MI unless otherwise specified. If the code is not identified in any admissions/deaths then they will be assumed to not have the outcome of interest.

Data sources

Scotland: SMR00 / SMR01 / NRS Deaths / Prescribing Information System / Scottish Blood Transfusion Database

England: Hospital Episode Statistics / Civil Registrations of Death / Medicines dispensed in Primary Care (NHSBSA data)

Outcome	Code (ICD-10 , OPCS4)
All-cause mortality	Any record of death.
Non-cardiovascular death (including fatal bleeding) and major non-fatal bleeding	
Death due to a non-cardiovascular cause
 
Primary position for cause of death
 
Ax, Bx, Cx, Dx Ex, Fx , Gx , Hx , Jx, Kx , Lx , Mx , Nx , Ox , Px , Qx , Rx , Sx , Tx , Ux , Vx , Xx , Yx , Zx.
 
OR
 
Hospitalisation for bleeding
 
Primary or first secondary position
 
I60x, I61x, I62x, S06.4x, S06.5x, S06.6x, K92.0x, K92.1x, K 92.2x, I85.0x, I98.3x, K22.6x, K25.0x, K25.2x, K25.4x, K25.6x, K26.0x, K26.2x, K26.4x, K26.6x, K27.0x, K27.2x, K27.4x, K27.6x, K28.0x, K28.2x, K28.4x, K28.6x, K29.0x, K62.5x, K66.1x, R58x, I23.0x, I31.2x, I69.0x, I69.1x, I69.2x, H21x, H35.6x, H31.3x, H43.1x, H44.8x, H45.0x, R04.0x, R04.1x, R04.2x, R04.8x, R04.9x, T81.0x, D62x, N83.7x, N93.8x , N93.9x, O03.1x, O03.6x, O04.1x, O04.6x, O05.1x, O05.6x, O06.1x, O06.6x, O20.8x, O20.9x, O46x , O67x, O07.1x, O07.6x, O08.1x, O71.7x , O72.0x , O72.1x , O72.2x , O90.2x , P26.1x , R31x , M25.0x.
 
OR

	
Primary procedure position (OPSC4)
 
E05x , E058x , E059x , F162x , D041x , E203x , F365x , G523x , H212x , H531x , K681x , P093x , P271x , T301x , Y221x , T032x , Y221x , T032x , Y321x , V032x , A052x , A053x , A054x , A103x , A401x , A411x

Non-cardiovascular death (including fatal bleeding)	
Primary cause of death
 
Ax , Bx , Cx , Dx , Ex , Fx , Gx , Hx , Jx , Kx , Lx , Mx , Nx , Ox , Px , Qx , Rx , Sx , Tx , Ux , Vx , Xx , Yx , Zx

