Major fatal and non-fatal bleeding	
Hospitalisation for bleeding
 
Primary or first secondary position
 
I60x, I61x, I62x, S06.4x, S06.5x, S06.6x, K92.0x, K92.1x, K 92.2x, I85.0x, I98.3x, K22.6x, K25.0x, K25.2x, K25.4x, K25.6x, K26.0x, K26.2x, K26.4x, K26.6x, K27.0x, K27.2x, K27.4x, K27.6x, K28.0x, K28.2x, K28.4x, K28.6x, K29.0x, K62.5x, K66.1x, R58x, I23.0x, I31.2x, I69.0x, I69.1x, I69.2x, H21x, H35.6x, H31.3x, H43.1x, H44.8x, H45.0x, R04.0x, R04.1x, R04.2x, R04.8x, R04.9x, T81.0x, D62x, N83.7x, N93.8x , N93.9x, O03.1x, O03.6x, O04.1x, O04.6x, O05.1x, O05.6x, O06.1x, O06.6x, O20.8x, O20.9x, O46x , O67x, O07.1x, O07.6x, O08.1x, O71.7x , O72.0x , O72.1x , O72.2x , O90.2x , P26.1x , R31x , M25.0x.
 
OR
 
Primary procedure position (OPCS4)
 
E05x , E058x , E059x , F162x , D041x , E203x , F365x , G523x , H212x , H531x , K681x , P093x , P271x , T301x , Y221x , T032x , Y221x , T032x , Y321x , V032x , A052x , A053x , A054x , A103x , A401x , A411x
 
OR
 
Death due to bleeding
 
Primary cause of death

	I60x, I61x, I62x, S06.4x, S06.5x, S06.6x, K92.0x, K92.1x, K 92.2x, I85.0x, I98.3x, K22.6x, K25.0x, K25.2x, K25.4x, K25.6x, K26.0x, K26.2x, K26.4x, K26.6x, K27.0x, K27.2x, K27.4x, K27.6x, K28.0x, K28.2x, K28.4x, K28.6x, K29.0x, K62.5x, K66.1x, R58x, I23.0x, I31.2x, I69.0x, I69.1x, I69.2x, H21x, H35.6x, H31.3x, H43.1x, H44.8x, H45.0x, R04.0x, R04.1x, R04.2x, R04.8x, R04.9x, T81.0x, D62x, N83.7x, N93.8x , N93.9x, O03.1x, O03.6x, O04.1x, O04.6x, O05.1x, O05.6x, O06.1x, O06.6x, O20.8x, O20.9x, O46x , O67x, O07.1x, O07.6x, O08.1x, O71.7x , O72.0x , O72.1x , O72.2x , O90.2x , P26.1x , R31x , M25.0x.

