Hospitalisation for bleeding	
Hospitalisation for bleeding
 
Primary or first secondary position
 
I60x, I61x, I62x, S06.4x, S06.5x, S06.6x, K92.0x, K92.1x, K 92.2x, I85.0x, I98.3x, K22.6x, K25.0x, K25.2x, K25.4x, K25.6x, K26.0x, K26.2x, K26.4x, K26.6x, K27.0x, K27.2x, K27.4x, K27.6x, K28.0x, K28.2x, K28.4x, K28.6x, K29.0x, K62.5x, K66.1x, R58x, I23.0x, I31.2x, I69.0x, I69.1x, I69.2x, H21x, H35.6x, H31.3x, H43.1x, H44.8x, H45.0x, R04.0x, R04.1x, R04.2x, R04.8x, R04.9x, T81.0x, D62x, N83.7x, N93.8x , N93.9x, O03.1x, O03.6x, O04.1x, O04.6x, O05.1x, O05.6x, O06.1x, O06.6x, O20.8x, O20.9x, O46x , O67x, O07.1x, O07.6x, O08.1x, O71.7x , O72.0x , O72.1x , O72.2x , O90.2x , P26.1x , R31x , M25.0x.
 
OR
 
Primary procedure position (OPCS4)
 
E05x , E058x , E059x , F162x , D041x , E203x , F365x , G523x , H212x , H531x , K681x , P093x , P271x , T301x , Y221x , T032x , Y221x , T032x , Y321x , V032x , A052x , A053x , A054x , A103x , A401x , A411x

Intracranial haemorrhage	
Intracranial haemorrhage event
 
Primary or first secondary position
 
I60x , I61x , I62x , S06.5x , S06.6x.

	
OR
 
Death due to intracranial haemorrhage
 
Primary cause of death
 
I60x , I61x , I62x , S06.5x , S06.6x.

Gastrointestinal bleeding	
Gastrointestinal bleeding event
 
Primary or first secondary position
 
K92.0x , K92.1x , K 92.2x , I85.0x , I98.3x , K22.6x , K25.0x , K25.2x , K25.4x , K25.6x , K26.0x , K26.2x , K26.4x , K26.6x , K27.0x , K27.2x , K27.4x , K27.6x , K28.0x , K28.2x , K28.4x , K28.6x , K29.0x , K62.5x , K55.2x , K66.1x.
 
OR
 
Death due to Gastrointestinal bleeding
 
Primary cause of death
 
K92.0x , K92.1x , K 92.2x , I85.0x , I98.3x , K22.6x , K25.0x , K25.2x , K25.4x , K25.6x , K26.0x , K26.2x , K26.4x , K26.6x , K27.0x , K27.2x , K27.4x , K27.6x , K28.0x , K28.2x , K28.4x , K28.6x , K29.0x , K62.5x , K55.2x , K66.1x.

Cardiovascular mortality and non-fatal myocardial infarction	
Death due to a cardiovascular cause
 
Primary cause of death
 
Ix
 
OR
 
Myocardial infarction after the Index Admission Discharge Date

	
Primary or first secondary position
 
I21x, I22x

Cardiovascular mortality (cardiac and non-cardiac)	
Death due to a cardiovascular cause
 
Primary cause of death
 
Ix

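### Three of the five outcomes with a bleeding code list take in the whole ICD-10 category H21x, where the other eye codes in the list are held to one subcode each

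*SAP*

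**What the plan says.** SAP section 4.6 names the secondary safety outcomes, among them "Major fatal and non-fatal bleeding", and refers to Appendix C for their definitions. Five of these outcomes have a list of bleeding codes there.

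In three of the five, the hospitalisation list contains "H21x, H35.6x, H31.3x, H43.1x, H44.8x, H45.0x". For major bleeding, the same run is also in the list of causes of death. A hospital code counts when it is in the "Primary or first secondary position"; a death code counts only as the primary cause.

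The two site-specific outcomes have their own lists. Intracranial haemorrhage uses "I60x , I61x , I62x , S06.5x , S06.6x". The gastrointestinal list holds only K and I codes and ends "K28.6x , K29.0x , K62.5x , K55.2x , K66.1x".

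SAP section 4.6.1 adds a sensitivity analysis of the safety outcomes in which the same codes count if they "occur in any diagnostic position".

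**The concern.** Within eye disease the list picks out single subcodes: one each under H35, H31, H43, H44 and H45. For H21 alone it takes everything. That looks like a dropped fourth character. If H21.0 is the only haemorrhage subcode in that category, admissions coded for other H21 conditions enter the outcome as bleeds.

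Nothing later in the plan removes them. Major bleeding uses the same hospital codes as hospitalisation for bleeding, with no severity criterion. Protocol section 7.1 says that bleeding events will be classified by the BARC definition, but Appendix C has no such step. The fourth check in SAP section 5 compares the codes in the datasets with the SAP, so it would reproduce an over-broad SAP code and not detect it.

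At stake is the clarity of the bleeding comparison. The protocol's hypothesis (section 1.8) is that the shorter duration is safer, and section 9.3 already expects few events.

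**Working it through.** **1. What the suffix means.** The SAP does not define x. Its use in Appendix C does: Ix stands for all cardiovascular causes of death, and I21x with I22x stands for myocardial infarction. H21x therefore means every code under H21.

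**2. Where H21x appears.** Reading each Appendix C list that contains bleeding codes:

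| Outcome | H21x in hospital list | H21x in death list |
|---|---|---|
| Non-cardiovascular death and major non-fatal bleeding | yes | no separate bleeding-death list |
| Major fatal and non-fatal bleeding | yes | yes |
| Hospitalisation for bleeding | yes | not applicable |
| Intracranial haemorrhage | no | no |
| Gastrointestinal bleeding | no | no |

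That is four lists and three of five outcomes. The same sequence, "I69.2x, H21x, H35.6x, H31.3x, H43.1x", recurs in each of the four, so an error in reading the PDF is unlikely.

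**3. Level of the eye codes.** There are six entries. H35.6x, H31.3x, H43.1x, H44.8x and H45.0x have a fourth character; H21x has none.

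**4. Size, by illustration.** The plan gives no figure to reproduce and no count of H21 admissions. Protocol section 9.2 cites a meta-analysis in which "the point estimates of the hazard ratios for all-cause mortality, non-cardiac mortality and bleeding were 0.87, 0.83 and 0.58 respectively", so 0.58 serves as the true bleeding ratio. The false shares of 2%, 5% and 10% are assumptions. The hazard ratio is approximated by the ratio of event counts in equal arms.

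*(a) q is the false share of all counted bleeds, split equally between arms.* Taking the total as 1, true events are (1−q)/1.58 in the 12-month arm and 0.58(1−q)/1.58 in the 3-month arm, and each arm gains q/2:

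observed ratio = [0.58(1−q)/1.58 + q/2] / [(1−q)/1.58 + q/2]

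- q = 0.02: (0.3597 + 0.0100)/(0.6203 + 0.0100) = 0.587
- q = 0.05: (0.3487 + 0.0250)/(0.6013 + 0.0250) = 0.597
- q = 0.10: (0.3304 + 0.0500)/(0.5696 + 0.0500) = 0.614

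*(b) f is the false share of counted bleeds in the 12-month arm only.* Then observed ratio = 0.58(1−f) + f:

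- f = 0.02: 0.5684 + 0.02 = 0.588
- f = 0.05: 0.5510 + 0.05 = 0.601
- f = 0.10: 0.5220 + 0.10 = 0.622

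Form (a) matches a statement about the share of all counted bleeds and is the one used in the conclusion. The choice changes little.

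**The case against.** The main objection is that the SAP prints no ICD-10 titles. That H21.0 is the haemorrhage subcode comes from the classification the SAP names, not from its text. The internal evidence is a mismatch of code level, and three-character entries are not rare in the same list (I60x, R58x, D62x, R31x, O46x, O67x). This stands in part. The mismatch is an anomaly among the eye codes and not proof, so the sponsor should check the manual before editing. Nor does this point establish that every other entry in the list is right.

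It is also fair to say that the affected outcomes are secondary, that SAP section 4.6 interprets them by effect size and interval, and that even a 10% false share would hardly change the reading of a ratio of 0.58. The death-list entry matters only if an H21 code is the primary cause of death.

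A reader might infer three stronger things, none of which the documents support:

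- **That every bleeding outcome is contaminated.** The intracranial and gastrointestinal lists omit H21x. The composite of non-fatal bleeding and all-cause mortality in SAP section 4.8 has no row in Appendix C, so whether it inherits the code is not stated.
- **That false events would fall unevenly between arms,** for example because elective eye surgery is deferred during dual therapy. The documents say nothing about eye surgery or its timing, and an imbalance could act in either direction.
- **That the edit can be made before linkage with no consequence.** SAP V2.0 is dated 4 June 2025, and neither document says whether linked outcome data have been seen.

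**Conclusion.** The point holds as a specific coding defect in three prespecified secondary safety outcomes. As written, any H21 code in the first two diagnostic positions counts as a major bleed, and the any-position analysis widens this. The planned quality control would not catch it.

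The conclusion rests on two readings: that x means all subcodes, which the SAP's own usage supports, and that H21.0 is the haemorrhage subcode, which needs confirming.

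The numerical effect is unknown and probably small. Under false shares of 2% to 10% of counted bleeds, unrelated to arm, a hazard ratio of 0.58 would show as about 0.59 to 0.61. These shares have no anchor in the documents. The direction under that assumption is towards no difference. All-cause mortality, intracranial haemorrhage and gastrointestinal bleeding are untouched. The case for acting is that the correction is simple, not that the bias is large.

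**What to change.** Check H21 against the ICD-10 manual. If H21.0 is confirmed as the haemorrhage subcode, replace H21x by H21.0x in all four Appendix C lists: the hospitalisation lists of the composite, of major bleeding and of hospitalisation for bleeding, and the death list of major bleeding. If the whole category is intended, give the reason in Appendix C. In the same edit, state which bleeding list the section 4.8 composite uses.

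Record the change as a dated SAP amendment that says whether linked outcome data had been seen by then. If they had, report the affected outcomes under both definitions.

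The cost is one code changed in four places, the matching change in the analysis programs and in any equivalent New Zealand code mapping, and the amendment itself.

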7 STUDY ASSESSMENTS

7.1 DATA COLLECTION AND OUTCOME ASSESSMENTS

Baseline patient characteristics, past medical history and medication use will be obtained from the randomisation database and data linkage from the participant's electronic health records.

Outcome measures for patients recruited in Scotland will be obtained through the Farr Institute in collaboration with the electronic Data Research and Innovation Service (eDRIS) and the General Register Office as we have successfully achieved with the SCOT-HEART [SCOT-HEART, 2015; Williams et al, 2016] and HighSTEACS [Shah et al, 2015a; Shah et al, 2015b] trials (Tables 2 and 3). We will capture all hospital admission events and will have access to clinical records and imaging as required through NHS Safe Havens. Outcome measures for patients recruited in England will be obtained through NHS Digital. We will record the following safety endpoints: all-cause death, non-cardiovascular death, fatal bleeding, major bleeding (including gastrointestinal and intracranial haemorrhage), hospitalization for bleeding (all ICD-10 coded), as well as blood transfusions, where possible). The bleeding data will be used to classify bleeding events using the standardized bleeding definition for cardiovascular clinical trials as defined by the Bleeding Academic Research Consortium (BARC) [Mehran et al, 2011]. We will record the following efficacy endpoints: all-cause death, cardiovascular (cardiac and non-cardiac) death, myocardial infarction (non-fatal and fatal) [Thygesen et al, 2012], stroke (non-fatal and fatal; thrombotic and haemorrhagic), coronary revascularisation (percutaneous coronary intervention and coronary artery bypass graft surgery), and stent thrombosis.

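### SAP Appendix C puts the whole ICD-10 category H21x in its bleeding lists, so non-bleeding iris disorders count as major bleeding (minor; secondary safety outcomes only)

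*SAP*

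**What the plan says.** SAP Appendix C defines outcomes by code: "Outcomes defined used the following codes and positions specified below following the date of index MI unless otherwise specified". For hospital events the diagnosis must be in "Primary or first secondary position". The column header names ICD-10 and OPCS4, and no titles are printed beside the outcome diagnosis codes.

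The run "H21x, H35.6x, H31.3x, H43.1x, H44.8x, H45.0x" stands in four lists across three outcome rows:

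- the hospitalisation list of the composite of non-cardiovascular death and major non-fatal bleeding;
- the hospitalisation list of "Major fatal and non-fatal bleeding";
- the cause-of-death list of that same outcome;
- the list for hospitalisation for bleeding.

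Protocol 7.1 describes a further classification step: "The bleeding data will be used to classify bleeding events using the standardized bleeding definition for cardiovascular clinical trials", meaning BARC. The SAP code lists apply no BARC grade, and Appendix C states no adjudication step. For the secondary safety outcomes, SAP 4.6.1 adds a sensitivity analysis that "will consider the occurrence of an event if the diagnostic codes, as defined in Appendix C, occur in any diagnostic position".

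**The concern.** The list is otherwise selective. It takes only the even-numbered subcodes .0 to .6 of K25 to K28, K29.0 rather than K29, K62.5 rather than K62, and single subcodes for the other eye entries. H21x breaks that pattern in a category that is not a bleeding category. Its other subcodes are conditions such as degeneration, cysts and adhesions of the iris.

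The hospitalisation list is the same in all three rows, so one such admission scores a false event in three safety outcomes at once. If non-bleeding iris disorders are unrelated to the length of antiplatelet therapy, these events pull the bleeding hazard ratios towards 1. Analysis is by time to first event (SAP 4.6), so a false event can also displace a later true bleed. Less bleeding is the expected advantage of the shorter arm, and protocol 9.3 already expects few events, so avoidable noise in the bleeding outcomes is worth removing.

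**Working it through.** No figure in the plan depends on this code, so there is nothing to reproduce. The check has three parts and an illustration.

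**1. Level of each code.** The diagnosis list for major bleeding has 76 entries. Nine have no fourth character: I60x, I61x, I62x, R58x, H21x, D62x, O46x, O67x and R31x. The other 76 − 9 = 67 have one. Of the six eye codes, only H21x is at category level.

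**2. Is category level a problem in itself?** No. SAP Appendix B labels I60x to I62x as haemorrhagic stroke. By their ICD-10 titles, R58, D62, O46, O67 and R31 are haemorrhage, post-haemorrhagic anaemia or haematuria categories. For these eight, the whole category fits the purpose of the list. H21 is the exception, because its bleed is confined to H21.0.

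**3. Does a later step catch it?**

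- Quality control item 4 in SAP section 5 checks that the codes in the datasets match the SAP. That would reproduce H21x faithfully.
- The any-position analysis in 4.6.1 widens the position and leaves the codes as they are. It can add such events but not remove them.
- Extended follow-up (4.9) repeats the secondary outcomes with the same definitions.
- The composite in 4.8 includes non-fatal bleeding but has no row of its own in Appendix C. It inherits the issue if it uses the same list.

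**4. Illustration of dilution.** Inputs:

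- Bleeding hazard ratio 0.58, cited in protocol 9.2 from a meta-analysis of stent trials.
- f, the share of counted events in the 12-month arm that are not bleeds. This is an assumption; the documents give no value.
- Non-bleeds are taken to have a hazard ratio of 1.

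Formulas: diluted HR = 0.58 × (1 − f) + 1 × f. Events for 80% power at two-sided 5% with 1:1 allocation = 4 × (1.960 + 0.842)² / (ln HR)².

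| Assumed f | Diluted HR | Events needed |
|---|---|---|
| 0 | 0.580 | 106 |
| 0.1% | 0.580 | 107 |
| 1% | 0.584 | 109 |
| 2% | 0.588 | 112 |
| 5% | 0.601 | 122 |

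For example, at f = 5%: 0.58 × 0.95 + 0.05 = 0.601. The 0.58 compares up to 6 months with 12 months, under other bleeding definitions, and does not describe the composite with non-cardiovascular death. The table shows only how the shift scales with f.

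**The case against.** The strongest objection is that Appendix C prints no code titles, so the statement that only H21.0 is a bleed comes from ICD-10 and not from the trial documents. That stands as a reason to check the edition before editing. It does not remove the point: the SAP defines its outcomes in ICD-10, so the title of a listed code is the content of the rule.

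Three stronger readings are tempting, and the documents do not support them.

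- *H44.8x is the same defect and should go.* It is already a four-character code, and it includes haemophthalmos, a true bleed, alongside other disorders of the globe. Dropping it trades sensitivity for specificity, which is a choice and not a correction.
- *The number of false bleeds can be estimated.* That would need a rate of non-bleeding H21 admissions and a rate of true bleeding admissions. The documents give neither, so any share would be one assumption divided by another.
- *The any-position analysis makes this materially worse.* It can only add H21 events, but nothing in the documents says how often iris disorders appear as secondary codes.

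It is also fair to say that the affected outcomes are secondary, and that SAP 4.6 interprets them by effect size and confidence interval without formal control of multiplicity.

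**Conclusion.** Wrong as written, and minor. H21x scores non-bleeding iris disorders as bleeding in three secondary safety outcomes, and in the 4.8 composite if that uses the same list. The conclusion rests on the ICD-10 content of H21, to be confirmed for the edition used.

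The size cannot be computed from the documents and is probably small. At an assumed non-bleed share of 1% to 5%, a hazard ratio of 0.58 would move to between 0.584 and 0.601. The cause-of-death list is unlikely to contribute, since an iris disorder would have to be the primary cause of death.

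A reader might infer that the trial's main result is at risk. It is not: all-cause mortality is any record of death, and the intracranial and gastrointestinal lists contain no eye codes.

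**What to change.** Confirm the content of H21 in the ICD-10 edition behind each data source. This includes New Zealand, whose sources Appendix C does not list. Then replace H21x with H21.0x in the four lists named above, and carry the change into the any-position analysis (4.6.1), the composite (4.8, if it shares the list) and extended follow-up (4.9).

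Keep H44.8x in the main definition. Optionally, add a sensitivity analysis without it and report bleeding events by code, so that readers can see what each code contributes.

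The cost is a short, documented amendment to a finalised SAP (V2.0), made in four places. If the H21 content is confirmed, no true bleed is lost.
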